3.2.1.1 Age 12-24 years

- 3.2.1.1.a** Patient aged 12-17 years: has signed informed assent and their parent/legal guardian has signed informed consent for study participation.
- 3.2.1.1.b** Patient aged 18-24 years: has signed informed consent for study participation.
- 3.2.1.2** Receiving allogeneic or autologous HCT for treatment of malignancy or bone marrow failure syndrome at Seattle Cancer Care Alliance (Seattle Children's Hospital and Fred Hutchinson Cancer Research Center), Children's Hospital Los Angeles (CHLA), University of Alabama at Birmingham (UAB) or St. Jude Children's Research Hospital (SJCRH).
- 3.2.1.3** Within 4 weeks of their HCT date ("day zero") (if prior, their planned HCT date)
- 3.2.1.4** Patient able to speak in the English language
- 3.2.1.5** Patient able to read in the English or Spanish language
- 3.2.1.6** Cognitively able to participate in interactive interviews

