If medications are dispensed in a blister package, if possible, study participants will be asked to place blister packages into medication bottles and take as above. Because most AYAs can take tablets, use of liquid formulations will be rare. However, when indicated or requested by patients, pharmacists will dispense oral, crushable tablets for compounding. Those study participants will, however, be asked to open their MEMS bottle at the same time as taking their GVHD medication. Patients will be instructed not to open the container unless taking a dose of the medication and to remove only the prescribed dose. After the final 6 months of study participation, study participants will be asked to return their MEMS track cap to their study coordinator.

9.6 Data collection schedule for study staff.

Caregiver reported costs of care and medical record data will be collected monthly (Figure 3). Details about staff-data collection are as follows:

Figure 3. Schedule of Study Activities by Month Post-Enrollment

Month	0	1	2	3	4	5	6
	P	P	P	P	B	B	B
	S				S		S
PRISM	PS	PS-a	PS-a	PS	PS-a	PS-a	PS
	M	M	M	M	M	M	M
	HR	HR	HR		HR		HR
	BS	BS			BS		
-Digital MEMS cap monitoring -							
Enrollment and Randomization	S			S			S
	PS	PS-a	PS-a	PS	PS-a	PS-a	PS
Usual Care	M	M	M	M	M	M	M
	HR	HR	HR		HR		HR
	BS	BS			BS		
-Digital MEMS cap monitoring -							

LEGEND: P=PRISM Session, B=PRISM Booster, S=Survey, PS = Parent Survey, PS-a = Parent Survey, abbreviated, M=Medical Record Abstraction, HR=Heart Rate Variability, BS = Blood Sample

9.6.1 Digital pharmaco-adherence. Medical record abstraction will include prescription details including medication-name, frequency, and dosing.

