9.6.2 Health care utilization. The Case Report Form (CRF, appendix) will capture the following variables through medical records and billing systems: (1) Intervention time: visit time related to case management and PRISM sessions; (2) mental health utilization: number, location, and duration of formal psychosocial clinician visits, psychological diagnoses, number of prescription psychiatric medications; and, (3) additional relevant utilization: number of supportive care medications (including acute and chronic pain medications and sleep-aids), number of and reason for unplanned hospital days, Emergency Department, outpatient clinic visits; resource use associated with additional health problems and diagnoses such as medical treatments and procedures, additional hospital services, distance between home and primary care facility (documented by home zip code), etc.

9.6.3 Additional covariates. RA's at each site will prospectively abstract the following clinical covariates from the medical record (using study-specific CRFs, appendix): the AYA's diagnosis, GVHD-directed treatments (and modifications), and treatment-intensity in the past month.⁹⁸ These variables were selected to capture relevant costs and based on prior evidence that AYA well-being and family psychosocial needs affect immediate psychosocial outcome metrics (e.g.,

psychological distress and quality of life).^{46,98} In addition, RAs at each site collecting biomarker data (i.e., heart rate variability and/or blood samples) will abstract additional clinical covariates to provide needed context as to the conditions under which the corresponding biologic data were collected. These data will only be collected for participants who consented to the HRV and/or CTRA optional components of the study. Sites collecting heart rate variability (HRV) data will abstract the following clinical information for participating patients: cardiac medications, diagnostic cardiac test data, and patient weight, height, and Body Mass Index (MBI). Sites collecting blood samples will abstract the following information for participating patients: date of conditioning chemotherapy and/or radiation start, transplant date, and blood test information.

9.7 Resilience in Pediatric Cancer Assessment (RPCA) Survey (both arms):

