9.9.3 Data Collection Schedule

HRV data and/or blood samples will be collected at clinically relevant and study specific time intervals where possible (**Table 6**). When not possible, HRV and/or blood sample data collection will be scheduled at the patient's convenience, and/or during the next scheduled clinical lab draw. .

Table 6. Biological data collection schedule

Time Point	T1 (Baseline)	T2 (PRISM session #1 OR 1 week post enrollment)	T3 1 month (survey timepoint)	T4 3 months (survey timepoint)	T5 6 months (survey timepoint)
24-hour HRV Recording	X	X	X	X	X
Blood Sample	X		X	X	

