11.5.4 **We will explore the relationship between biomedical variables and patient reported anxiety and depression** through a combination of paired and unpaired t-tests, chi-squared (or Fisher's exact) tests, and linear and logistics regression. DNE will be defined as the number of days from transplant to an absolute neutrophil count (ANC) of >500/mm³ for >3 days. Cumulative incidence and severity of Grade II-IV GVHD will be defined by the revised Seattle Criteria as documented by the patient's clinical provider. HRV will be measured in 24-hour increments using both time and frequency domain parameters as established by the international Cardiology task force guidelines. Means and standard deviations will be compared to published normative data in adolescents. CTRA scores will be divided into two groups (above and below the median). We will perform multivariable analyses, adjusting for age, sex, diagnosis, disease status at the time of transplant, conditioning intensity, and,

immunosuppressive medications/GVHD prophylaxis to examine the association between CTRA biology and HCT outcomes.

11.6 Additional analyses, confounders, and other considerations.

We will conduct interaction modeling and subgroup analyses to explore whether the effect of the intervention is modified by medical covariates, symptom distress, and/or adherence. The rationale for these subgroup analyses is grounded in prior findings suggesting symptoms, adherence, and overall well-being are associated.¹⁴⁰

We will conduct a thorough process evaluation that includes: (a) intervention fidelity; and, (b) satisfaction queries. Multiple comparisons are a concern since we are collecting multiple measures from patients and are interested in several hypotheses. We minimize this problem by specifying a limited number of main hypotheses for each aim. The Benjamini-Hochberg procedure will be used to control the False Discovery Rate criterion at $\alpha=0.05$ to correct for multiple testing in analyses that are not pre-specified.¹⁴¹ Likewise, in manuscripts and presentations, we will report the number of tests performed and interpret results within this context.

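### The CTRA models in 11.5.4 leave out days from transplant to the blood draw, although each sampling timepoint, counted from enrolment, spans about 56 days of transplant time

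*Combined protocol and SAP*

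**What the plan says.** **Enrolment.** Section 3.2.1.3 admits patients "Within 4 weeks of their HCT date", and the bracketed addition "if prior, their planned HCT date" shows that enrolment may come before or after day zero.

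**Sampling clock.** Figure 3 in section 9.6 is headed "Schedule of Study Activities by Month Post-Enrollment". Table 6 in section 9.9.3 ("Biological data collection schedule") puts blood samples at baseline, 1 month and 3 months and ties the later draws to survey dates, for example "T3 1 month (survey timepoint". If a planned time is not possible, the draw may move to suit the patient "and/or during the next scheduled clinical lab draw".

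**Assay.** Sections 9.9.2 and 13.6 specify whole blood. Section 13.7.5 describes mapping and transcript counts and mentions no step for cell composition.

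**Model.** Section 11.5.4 splits CTRA scores at the median and relates CTRA to HCT outcomes in multivariable models "adjusting for age, sex, diagnosis, disease status at the time of transplant, conditioning intensity", plus immunosuppressive medication or GVHD prophylaxis. It does not say which of the three samples is used.

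**Available data.** Section 9.6.3 has sites that draw blood abstract "date of conditioning chemotherapy and/or radiation start, transplant date, and blood test information", so that the conditions of sampling are known. Section 11.5.4 does not mention these variables.

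**The concern.** Whole-blood RNA comes from whichever leukocytes are circulating at the draw. In HCT that mix changes with conditioning, aplasia and engraftment. With the clock started at enrolment, one patient's baseline sample may precede conditioning while another's follows engraftment, and both enter the same median split.

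The models in 11.5.4 compare patients by CTRA level, not by randomised arm, so randomisation does not protect them. If transplant phase shifts the CTRA score and is also related to the outcome, the estimated association is confounded, and no listed covariate measures phase at the draw.

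Neutrophil engraftment raises a further problem. It is defined from the absolute neutrophil count. A sample taken after engraftment cannot predict it, and one taken during aplasia may be tied to it mechanically. The plan excludes neither.

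**Working it through.** The documents give no sample size, variance or power figure for CTRA, so there is no stated figure to reproduce. The check is date arithmetic followed by a sensitivity range.

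**1. Transplant day at each draw**

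Inputs: enrolment day E from -28 to +28 (3.2.1.3); offsets of 0, about 30 and about 91 days (Table 6, months converted to days). Formula: day from HCT = E + offset.

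| Draw | Earliest | Latest | Span |
|---|---|---|---|
| Baseline | -28 + 0 = -28 | 28 + 0 = +28 | 56 days |
| 1 month | -28 + 30 = +2 | 28 + 30 = +58 | 56 days |
| 3 months | -28 + 91 = +63 | 28 + 91 = +119 | 56 days |

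These are nominal dates. If the baseline draw used the two weeks allowed for the baseline survey (9.3.2), baseline would run to 28 + 14 = +42. If later draws used the survey window of 28 days either side (9.7), 1 month would run from 2 - 28 = -26 to 58 + 28 = +86, and 3 months from 63 - 28 = +35 to 119 + 28 = +147. That draws follow the survey windows is an assumption.

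**2. Share of 1-month draws still early after HCT**

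Assumptions, not in the documents: E is uniform over its range, and engraftment is on day w = 14, 21 or 28. The share drawn by day w is (w - 2)/56 if enrolment covers the whole window, and (w - 2)/28 if everyone enrols before HCT.

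| w | Whole window | All before HCT |
|---|---|---|
| 14 | 12/56 = 21% | 12/28 = 43% |
| 21 | 19/56 = 34% | 19/28 = 68% |
| 28 | 26/56 = 46% | 26/28 = 93% |

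At baseline, with the whole window, 28/56 = 50% precede HCT. Between HCT and engraftment lie 14/56 = 25% (w = 14) to 28/56 = 50% (w = 28), and the remaining 25% to 0% follow engraftment. At 3 months, nominal sampling starts at day +63, so no draw falls in these windows.

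**3. How much CTRA variance phase could explain**

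Assume a shift of d residual SDs in samples drawn between HCT and engraftment on day 21. With p the proportion of such samples, the variance share is v/(1 + v), where v = d² × p(1 - p).

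- Baseline: p = 21/56 = 0.375, so p(1 - p) = 0.234.
- 1 month: p = 19/56 = 0.339, so p(1 - p) = 0.224.

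| d (SD) | Baseline | 1 month | 3 months |
|---|---|---|---|
| 0.25 | 1% | 1% | 0% |
| 0.5 | 5.5% | 5.3% | 0% |
| 1 | 19% | 18% | 0% |
| 2 | 48% | 47% | 0% |
| 3 | 68% | 67% | 0% |

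Phase would account for more than half of the variance only if d exceeded 1/√0.234 = 2.07 SD at baseline or 1/√0.224 = 2.11 SD at 1 month. The documents neither give d nor rule out any of these values.

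**The case against.** **The authors foresaw the issue.** Section 9.6.3 collects the transplant and conditioning dates to give context to the samples. That is true, but the model in 11.5.4 does not use them. The gap is small and is in the analysis text.

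**Randomisation covers part of it.** For PRISM versus usual care, draw timing is balanced in expectation, so the cost there is noise and chance imbalance. This stands, and it limits the bias concern to the CTRA-outcome associations.

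**Transplant type is largely covered.** The exclusion for the adherence component (3.2.2) describes autologous recipients as not receiving standard GVHD prophylaxis, so the prophylaxis term in the model mostly separates the two groups. This stands. Transplant type is not a further omission worth pressing.

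**A large adjustment set would overfit.** CTRA is optional (3.1) and collected only in Seattle (13.1). Table 3 projects 11 enrolments a year there, or 11 × 3 = 33 over 36 months; section 25.0 anticipates 50-60 locally. Both figures precede opt-in. Cell composition might also lie on a path from stress to CTRA, so forcing it into every model could remove signal. This stands too, and is why counts belong in a sensitivity analysis.

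**Stronger readings that the documents do not support.**

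- A reader might infer that CTRA will mainly reflect marrow recovery. No passage says how CTRA varies with counts or engraftment, and step 3 shows that this would need a shift above about 2 SD. The 3-month draw falls outside the assumed windows.
- A reader might infer that leukocyte counts are already collected for each draw. Section 9.6.3 refers to blood tests without itemising them and names no count, differential or same-day requirement.
- A reader might infer that samples will be lost by phase because aplastic blood yields too little RNA. Sections 9.9.2 and 13.7.5 mention mass and integrity checks but give no threshold or expected failure rate.

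**Conclusion.** The point holds as a limited one. Each nominal CTRA timepoint covers about 56 days of transplant time, which follows directly from the eligibility window and Table 6. The models in 11.5.4 ignore time from HCT to the draw although the transplant date is abstracted. The non-randomised associations of CTRA with HCT outcomes may therefore be confounded by transplant phase and cell composition, chiefly at baseline and 1 month, and engraftment models that include post-engraftment samples cannot be read as prediction.

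The amount of confounding is unknown. The 21-46% of 1-month draws by day +14 to +28 rests on uniform enrolment over the whole window and assumed engraftment days. The variance shares also rest on an assumed shift. Nothing here affects the primary or secondary outcomes; CTRA belongs to a descriptive exploratory aim (1.5.2). It is worth correcting because the main variable needed is already collected.

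**What to change.** In section 11.5.4:

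1. Add days from HCT to the draw, or transplant phase at the draw, to the CTRA models. A straight-line day term may miss a fall and recovery, so phase may fit better. If the subset is too small for another term, state in advance which listed term it replaces.
2. State which sample (baseline, 1 month or 3 months) is used for each outcome and for the median split.
3. Limit models of CTRA against neutrophil engraftment to samples drawn before conditioning starts, or at least before HCT.
4. Use the white count and differential nearest the draw only as a prespecified sensitivity analysis, after confirming that the blood tests abstracted under 9.6.3 include them. If they do not, this step needs extra chart abstraction.

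Steps 1 to 3 change wording only and use dates already abstracted. The cost is one more model term (two parameters if phase has three levels) and fewer samples for the engraftment analysis: about half of baseline samples precede HCT under uniform enrolment, and no more than that precede conditioning.

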11.7 Missing Outcome Data

While our goal will be to minimize missing data, data may still be missing due to patients/families skipping individual survey items, omissions in medical records, lack of follow-up, medical complications, or death. We will quantify the amount of missing data, evaluate the pattern of missingness, association of participant characteristics with missing data, and minimize bias and increase efficiency in the associations of interest by applying appropriate methods to account for missing data.¹⁴²⁻¹⁴⁴ For example, for outcomes where missing at random (MAR) is a plausible assumption, we will use multiple imputation or inverse probability weighting, depending on the statistical model being considered. For missing not at random (MNAR) data, we will use sensitivity analyses. In all cases, we will assess the robustness of estimates due to assumptions.

12.0 Confidentiality

- 12.1 Data Storage.** All information and biospecimens collected for research purposes will be coded. Identifying information (names, addresses and phone numbers) will be used initially only to identify potential patients to approach. The only link between the Participant identifiers and their study identifier will be kept on a password protected database and in a locked filing cabinet. There are no patient identifiers collected and retained for research purposes. Feasibility data will represent only frequencies and percentages.
- 12.2 Patient Identifiers within stored data.** No participant identifiers will be kept with or included in the study data. All identifying patient information will be stored on a secure database, or in a locked filing cabinet with the study team. This data will be stored and

maintained for a minimum of ten years or until final analyses are completed, whichever occurs last, in order to ensure data quality.

12.3 Study-wide data management. Individual sites will be responsible for original source data (surveys, Case Report Forms) until study completion. All such materials will be stored in a locked file cabinet or other office with access only to study staff. Blood samples sent to UCLA for analysis will not contain any participant identifying information, they will be labeled with study ID only. When sample analysis is complete at UCLA, results containing study ID only will be faxed or scanned to the coordinating center for electronic storage. Upon study completion (last data collection for last patient), all materials will be coded (labeled only with study id) and faxed or scanned to the coordinating center for electronic storage.

As described above, monthly site data collection responsibilities will include monitoring of local data completeness and troubleshooting with the coordinating center for data completion, if necessary. Per the Data Transfer Agreement, a Limited Data Set will be transmitted by Seattle Children's research staff to external collaborators using a secure institutionally-approved method. Any data provided from SCH to [name] and DFCI for oversight purposes during active data completion will also be deidentified. Individual site teams will make all study files available during the on-site monitoring of the study by the coordinating site. In this instance, PHI will be viewable by the monitor for data accuracy but will not be copied or stored.

When Zoom is used, the following actions will be taken to protect confidentiality and privacy:

1. The latest version of Zoom that is available will be used.
2. The meeting room will be set to private.
3. A password/passcode will be required for meeting entry.
4. The private chat function will be disabled.
5. The General chat function will be used. Examples of General chat use may include sharing approved resources and PRISM app passwords, communicating if there are technical difficulties, and the accommodation of specific needs by participant's request (e.g. if a patient has a medical reason that may impact verbal communication).

13.0 Provisions to Monitor the Data to Ensure the Safety of Subjects

13.1 Data collection:

Data collection will occur at each of the enrolling study sites: Seattle Cancer Care Alliance (Seattle Children's Hospital and Fred Hutchinson Cancer Research Center), Children's Hospital Los Angeles (CHLA), University of Alabama at Birmingham (UAB) and St. Jude Children's Research Hospital (SJCRH), with the exception of CTRA gene

expression, which will only be collected at the Seattle site. Data collection will consist of self-report questionnaires and electronic ECG recordings from HRV monitors. Research material collected will be in the form of data from standardized questionnaires, digital ECG files, and also from medical record information extracted from the patient's electronic medical record. Protected health information (PHI) is accessible only by the site PIs and key study personnel.

13.2 Data Management

Research material collected will be in the form of data from the standardized questionnaires, medical record information, digital ECG files, blood samples, and electronic MEMs cap medicine adherence data. Protected health information (PHI) is accessible only by the site PIs and key study personnel, and the on-site monitor from the coordinating site (SCH). A variety of measures will be utilized to ensure participant privacy. Minimal paper records, such as consent forms, will be kept in a locked drawer in the site PIs' research offices. No identifiable patient information will be labeled on the surveys, blood samples, or ECG files; all will be identified with a study-specific identifier with assigned identifier kept on a password protected encrypted server. Data will be stored in an electronic database (REDCap -Research Electronic Data Capture) using the participant's study identifier. REDCap data collection projects rely on a thorough study-specific data dictionary defined as an iterative self-documenting process by all members of the research team. We have conducted the iterative development and testing process previously, resulting in well-planned data collection. REDCap servers are housed in a data center and all web-based information transmission is encrypted. For the present study, we will use the REDCap system managed by the University of Washington Institute for Translational Health Sciences (ITHS). REDCap was developed specifically around HIPAA-Security guidelines and is recommended to researchers at various institutions by both Privacy Officers and Institutional Review Boards. REDCap has been disseminated for use locally and at other institutions and currently supports over 300 academic/non-profit consortium partners on six continents and over 20,000 research end-users (www.project-redcap.org). The REDCap data record may contain some identifying information. Subjects will be tracked using their study identifier. The identifiable data will be designated as "PHI" in the REDCap database which will allow us to exclude access to the identifiable information as necessary.

13.3 Survey data

The study questionnaire ("Resilience in Pediatric Cancer Assessment", RPCA) and the intervention ("Promoting Resilience in Stress Management", PRISM) may address sensitive matters. Participants may be prompted to think about the threat to their life posed by their cancer, as well as other difficult topics such as psychological distress, grief, bereavement, and health behaviors. The topics to be covered may provoke sadness, anxiety, depression, fear or doubt.

While surveys will be coded to protect anonymity and do not include instruments to directly measure suicidal ideation or other self-harming behaviors, they will be reviewed within 72 hours for (a) missingness (see 13.4.1 below); and (b) unanticipated immediate threats to participants' or others' safety.

As part of the informed consent process, participants will be made aware of the survey-review timeline, as well as the fact that confidentiality may be broken in the case that providers see an immediate threat to the patient's or another's safety. No physical risks are expected to arise from the study.

If indicated, referral for consultation will include a direct phone call (or in-person consultation) by PI or research team member to recommend further help. This would include alerting: a) current therapist (if they have one), and b) their oncology social worker. The participant will also be given the phone number to the site's outpatient psychiatric clinic, and county-specific crisis line phone numbers will also be provided as needed.

In the event of other concerns from interventionists and/or other study staff based on interactions with AYAs and families, as well as in other cases of concern for patient or others' safety, the same processes will occur, including immediate referrals to the site PI, and the patients' primary medical and social work teams for in-person evaluation or referral to the appropriate mental health professional if warranted. After hours, the site PI and on-call providers from the medical teams will be notified. All study-related concerns for patient or other person's safety will be reported as an adverse event (AE) to the IRB and Data Safety Monitoring Committee (DSMC, see "Data Safety Monitoring Plan"), within 1 week of study staff awareness. In addition, the PI will review the potential risks and reported findings at least once monthly with study staff from all participating sites. While this is not a pharmacologic trial and we do not anticipate medical complications, sites will nevertheless notify the IRB and DSMC of all participant deaths at the time of study renewal (annually). Unanticipated (non-medical) participant deaths will be reported to the DSMC within 1 week with a determination if the event might be attributable to the study. In such cases, the DSMC chair may convene the committee and/or suspend the study for additional review (see section 13.5 below).

